7.2.1. Withdrawal From the Use of Research Samples

Withdrawal From the Use of Samples in Future Research

The participant may withdraw consent for use of samples for future research (refer to Long-Term Retention of Samples for Additional Future Research in Appendix 3). In such a case, samples will be destroyed after they are no longer needed for the clinical study. Details of the sample retention for research are presented in the main ICF.

7.3. Lost to Follow-up

A participant will be considered lost to follow-up if the participant repeatedly fails to return for scheduled visits and is unable to be contacted by the study site. A participant cannot be deemed lost to follow-up until all reasonable efforts made by the study-site personnel to contact the participant are deemed futile. The following actions must be taken if a participant fails to return to the study site for a required study visit:

- The study-site personnel must attempt to contact the participant to reschedule the missed visit as soon as possible, to counsel the participant on the importance of maintaining the assigned visit schedule, to ascertain whether the participant wishes to or should continue in the study.
- Before a participant is deemed lost to follow-up, the investigator or designee must make every reasonable effort to regain contact with the participant (where possible, 3 telephone calls, e-mails, fax, and, if necessary, a certified letter to the participant's last known mailing address, or local equivalent methods. These contact attempts should be documented in the participant's medical records.
- Should the participant continue to be unreachable, they will be considered to have withdrawn from the study.

Should a study site close, eg, for operational, financial, or other reasons, and the investigator cannot reach the participant to inform them, their contact information will be transferred to another study site.

8. STUDY ASSESSMENTS AND PROCEDURES

Overview

The Schedule of Activities summarizes the frequency and timing of study visits and of immunogenicity and safety measurements applicable to this study.

If multiple assessments are scheduled for the same timepoint, it is recommended that procedures be performed in the following sequence: vital signs, other safety assessments, blood draws. If needed, assessments may be performed at another day within the applicable visit window. Actual dates and times of assessments will be recorded in the source document and/or the eCRF.

Participants will be provided a thermometer (to measure body temperature), ruler (to measure local injection site reactions), and participant diary to record body temperature and solicited local (injection site) and systemic signs and symptoms.

The participant diary includes instructions on how to capture the data and grading scales to assess severity of the signs and symptoms. The study staff is responsible for providing appropriate training to the participant to avoid missing or incorrect data. The participant diary will be reviewed by the study-site personnel at the visit indicated in the Schedule of Activities.

The total blood volume to be collected from each participant will be approximately 30 mL.

Repeat or unscheduled samples may be taken for safety reasons or for technical issues with the samples.

Visit Windows

For the following visits, windows will be allowed as indicated:

Clinic	Visit	Visit	
Visit #	Day	Window	Primary Purpose
3	8	± 2 days	7 days after study vaccination, Safety visit, by telephone
4	15	-3 days / +7 days	14 days after study vaccination, Immunogenicity and Safety visit
5	29	\pm 7 days	28 days after study vaccination, Safety visit, by telephone
6	183	\pm 14 days	6 months after study vaccination, Immunogenicity and Safety visit

The timings of the post-vaccination visits will be determined relative to the actual day of study vaccination.

Sample Collection and Handling

The actual dates and times of sample collection must be recorded in the eCRF or laboratory requisition form.

Refer to the Schedule of Activities for the timing and frequency of all sample collections.

Instructions for the collection, handling, storage, and shipment of samples are found in the laboratory manual that will be provided. Collection, handling, storage, and shipment of samples must be under the specified, and where applicable, controlled temperature conditions as indicated in the laboratory manual.

Study-Specific Materials

The investigator will be provided with the following supplies:

- IB for Ad26/protein preF RSV vaccine (IB Ad26/protein preF RSV vaccine 2021)
- Study Site Investigational Product and Procedures Manual
- Laboratory manual

- Investigational Product Preparation Instructions
- Participant diary and instructions for use
- Ruler (to measure diameter of any erythema and swelling)
- Thermometer
- Laboratory kits
- Contact Information page(s)
- Study protocol
- IWRS Manual
- Electronic data capture (eDC) Manual/eCRF completion guidelines
- Wallet card
- Sample ICF

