The changes made to the clinical protocol VAC18193RSV3003 as part of Protocol Amendment 2 are listed below, including the rationale of each change and a list of all applicable sections. Changes made in previous protocol amendments are listed in Section 10.7 Appendix 7: Protocol Amendment History.

Section Number	Description of Change	Brief Rationale		
and Name				
Title page	Inclusion Criterion 3 was amended to	To facilitate enrollment		
1.1 Synopsis	expand the eligible age range from 60			
4.1 Overall Design	to less than 65 years, to 60 to 75			
5.1 Inclusion Criteria	years inclusive.			
5.2 Exclusion Criteria	Exclusion Criterion 10 was amended to allow the use of viral-vectored SARS-CoV-2 vaccines if administered at least 6 months prior to randomization.	To facilitate enrollment		
5.2 Exclusion Criteria	Footnote for Exclusion Criterion 13 was updated to allow participants who participate in the observational phase of interventional studies to be enrolled in the study, if approved by the sponsor or its delegate.	To facilitate enrollment		
5.2 Exclusion Criteria	A textual change was made to Exclusion Criterion 1 to clarify that participants with a history of malignancy within 5 years before screening, which is considered to have minimal risk of recurrence per investigator's judgement, can be enrolled.	Clarification		
5.2 Exclusion Criteria	Exclusion Criterion 7 was amended to restrict the exclusion of participants on treatment with immunoglobulins to those immunoglobulins expected to impact the vaccine-induced immune response.	Clarification		
1.3 Schedule of Activities	It was clarified that risk factors for blood clotting events and thrombocytopenia are to be collected and documented as part of the medical history at screening.	Clarification		
1.3 Schedule of Activities	It was clarified that the severity of solicited and unsolicited AEs and the occurrence of special reporting situations are to be assessed also during the phone call visits at 7 and 28 days post-vaccination, following the recording period specified for these events.	Clarification		

CONFIDENTIAL – FOIA Exemptions Apply in U.S.

VAC18193 (Ad26.RSV.preF [JNJ-64400141]/RSV preF Protein [JNJ-64213175]) Clinical Protocol VAC18193RSV3003 Amendment 2

Section Number Description of Change Brief Rationale						
and Name	2 osoripiion or enunge					

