- j. AESIs, including potential AESIs, are to be reported to the sponsor from the moment of vaccination until 6 months after the vaccination. See Section 8.3.6.
- k. Concomitant therapies will be collected from the time of study vaccination through 28 days post-vaccination when associated with an AE, and from ICF signature until 6 months post-vaccination when associated with an SAE or AESI.
- 1. Any history of SARS-CoV-2 vaccination (name/manufacturer of the vaccine and date of administration, whenever possible) prior to and during the study will be collected in the eCRF.
- m. Rulers and thermometers will be distributed at Visit 2.

- n. Participants will be contacted by telephone 2 to 4 days post-vaccination to remind them to fill in the participant diaries and to check that they are entering information correctly.
- o. Aliquots of serum samples collected for immunogenicity tests can be reconverted for participant's safety purposes upon sponsor request. Please refer to Table 4 for a non-exhaustive list of tests that may be requested to be performed on these samples in case of potential AESI reporting.
- p. Includes the assessment of the severity of solicited AEs during the Visit 3 phone call.

q. Includes the assessment of the severity of unsolicited AEs and the occurrence of special reporting situations during all visits up to 28 days post-vaccination, including the Visit 3 and Visit 5 phone calls.

AE = adverse event; AESI = adverse event of special interest; d = days; ICF = informed consent form; mo = months; SAE = serious adverse event; SARS-CoV-2 = Severe Acute Respiratory Syndrome Coronavirus-2; vac = vaccination

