8.3.1. Time Period and Frequency for Collecting AE, SAE, and AESI Information

All AEs

AEs and special reporting situations, whether serious or non-serious, that are related to study procedures or that are related to non-investigational sponsor products will be reported from the time a signed and dated ICF is obtained until the end of the study/early withdrawal.

Clinically relevant medical events not meeting the above criteria and occurring between signing of ICF and moment of vaccination will be collected on the Medical History eCRF page as pre-existing conditions.

Solicited AEs, collected through a participant diary, will be recorded from the time of vaccination until 7 days post-vaccination.

All other unsolicited AEs and special reporting situations, whether serious or non-serious, will be reported from the time of vaccination until 28 days post-vaccination.

All SAEs and AEs leading to discontinuation from the study (regardless of the causal relationship) are to be reported from the moment of vaccination until completion of the participant's last study-related procedure, which may include contact for safety follow-up. The sponsor will evaluate any safety information that is spontaneously reported by an investigator beyond the time frame specified in the protocol.

See Section 7.2 for procedures associated with withdrawal of consent.

All AEs will be followed until resolution or until clinically stable.

SAEs

All SAEs occurring during the study must be reported to the appropriate sponsor contact person by study-site personnel immediately, but no later than 24 hours of their knowledge of the event.

Information regarding SAEs will be transmitted to the sponsor using the SAE Form and Safety Report Form of the eCRF, which must be completed and reviewed by a physician from the study site, and transmitted to the sponsor immediately but no later than within 24 hours. The initial and follow-up reports of an SAE should be transmitted electronically or by facsimile (fax). Telephone

reporting should be the exception and the reporter should be asked to complete the appropriate form(s) first.

AESIs

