5.5. Safety Analyses

Safety endpoints (secondary endpoints):

- Solicited local (injection site) and systemic adverse events (AEs) for 7 days after vaccination
- Unsolicited AEs for 28 days after vaccination
- Serious adverse events (SAEs) and adverse events of special interest (AESIs) until 6 months after vaccination

Safety analyses will be performed on the FAS. Continuous variables will be summarized using the following statistics, as appropriate: number of observations, median, minimum, and maximum. Frequencies and percentages (one decimal place) will be generated for categorical variables. No formal comparisons between groups will be provided.

Safety data will be analysed and presented by study intervention, and if appropriate, by phase, and also across the entire study period where applicable. For unsolicited AE, the denominator for the percentages is the number of participants in the considered population and phase for a certain regimen (incidence per 100 participants/phase). For solicited AEs, the denominator for the percentages is the number of participants with data assessed by the investigator in the considered population and phase for a certain regimen (incidence per 100 participants/phase).

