5.5.1.4. Missing Data

Missing data will not be imputed. Participants who do not report an event will be considered as participants without an event. An AE with a missing severity or relationship will be considered as an AE reported, but will be considered as not reported for the severity or relationship. For example, an AE with missing severity will be considered as an AE reported for the analysis of any grade, but will be considered as not reported for the analysis of at least grade 3. The analysis of solicited AEs will include the safety data as documented by the investigator.

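### The call that closes the 28-day unsolicited-AE period may be made as early as Day 22, leaving up to 7 of 28 days without scheduled questioning

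*Protocol*

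**What the plan says.** **Endpoint.** SAP Section 5.5 lists "Unsolicited AEs for 28 days after vaccination" among the secondary safety endpoints. Protocol Section 8.3.1 sets the matching collection period: "All other unsolicited AEs and special reporting situations, whether serious or non-serious, will be reported from the time of vaccination until 28 days post-vaccination".

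**Contacts.** Protocol Section 8 (Visit Windows) and the Schedule of Activities put Visit 5 on Day 29 ± 7 days; Section 8 gives its purpose as "28 days after study vaccination, Safety visit, by telephone". Section 8 adds: "The timings of the post-vaccination visits will be determined relative to the actual day of study vaccination". Footnote q of the Schedule has unsolicited AEs assessed "during all visits up to 28 days post-vaccination, including the Visit 3 and Visit 5 phone calls", which makes Visit 5 the last of these contacts. Protocol Section 2.3.3 describes the 6-month follow-up as being for SAEs and AESIs. No text requires a second call after an early one.

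**Analysis.** SAP Table 3 closes the post-dose period at the later of 28 days and the 28-day visit, unless the participant leaves or the data are cut earlier. On percentages, SAP Section 5.5 states: "For unsolicited AE, the denominator for the percentages is the number of participants in the considered population and phase for a certain regimen". SAP Section 5.5.1.4 adds: "Participants who do not report an event will be considered as participants without an event".

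**The concern.** The endpoint has a fixed length of 28 days, but the length of scheduled questioning depends on when the site telephones. An early call ends the questioning and does not shorten the period over which the participant is counted. The days after the call are then scored as event-free, although nobody was scheduled to ask about them.

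At stake is the completeness of the 28-day rate of non-serious unsolicited AEs. Call scheduling could lower that rate, and the planned tables would not show it.

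**Working it through.** The plan gives no computed figure on this point, so the check is calendar arithmetic. SAP Section 5.1.1 numbers the vaccination date as Day 1, so Day 29 is 28 days after vaccination, which agrees with the plan's label for Visit 5.

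**Inputs from the documents:** Visit 4 on Day 15 (-3/+7), Visit 5 on Day 29 (± 7), Visit 6 on Day 183 (± 14), endpoint length 28 days, 250 participants per group.

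1. Earliest compliant call: 29 - 7 = Day 22, or 21 days after vaccination. Latest: 29 + 7 = Day 36, or 35 days after vaccination.
2. Largest uncovered share: (28 - 21)/28 = 7/28 = 25.0%. Counting Day 1 to Day 29 as 29 calendar days gives 7/29 = 24.1%.
3. Overlap with Visit 4: its window ends on 15 + 7 = Day 22, the day the Visit 5 window opens. Both contacts can fall on the same day, and the closing call would then add no observation time.
4. Next scheduled contact: Visit 6, Days 169 to 197, which is 169 - 22 = 147 to 197 - 22 = 175 days after a Day 22 call.

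**Average loss.** The documents give no distribution of call days, so these are assumptions:
- Uniform over Days 22 to 36 (15 days): 7/15 = 47% are called early. Mean loss is (1+2+...+7)/15 = 28/15 = 1.9 days, and 1.87/28 = 6.7%.
- Uniform within ± 3 days (7 days): 3/7 = 43% are called early. Mean loss is (1+2+3)/7 = 0.86 days, and 0.86/28 = 3.1%.

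**Effect on a reported rate.** The documents give no AE rate, so the true 28-day incidence p is assumed, with a constant hazard and no spontaneous reporting. If every call were on Day 22, the observed incidence would be 1 - (1 - p)^(21/28):

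| Assumed p | Observed | Missed per 250 |
|---|---|---|
| 5% | 3.8% | 3.1 |
| 10% | 7.6% | 6.0 |
| 20% | 15.4% | 11.5 |
| 30% | 23.5% | 16.3 |
| 40% | 31.8% | 20.4 |

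With uniform call days and p = 20%, the missed share is (1/15) × the sum over k = 1 to 7 of [0.8^((28-k)/28) - 0.8] = 0.012. The observed incidence is then 18.8%, and about 3 per 250 are missed.

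**The late side.** Calls on Days 30 to 36 extend the post-dose period in SAP Table 3 by 1 to 7 days. Under the uniform assumption that adds (1+2+...+7)/15 = 1.9 days on average, the same number that early calls remove. Active ascertainment can therefore run from 21 to 35 days.

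**The case against.** The strongest reply is that a day without a scheduled question can still yield a report. The duty to report runs to 28 days whenever the call is made. Protocol Section 8.3 has participants reporting AEs throughout the study. The SAP allocates events by onset date (Section 5.5.1.3), so a Day 25 event mentioned at Visit 6 would still belong to the post-dose period. SAEs and AEs leading to discontinuation are reported until the last study procedure, AESIs for 6 months, and procedure-related AEs to study end. All of this stands, and it narrows the gap to non-serious, non-AESI events with onset after an early call. Those depend on the participant volunteering them, possibly about five months later. A report that late would also miss the primary analysis, and Protocol Section 9.5 names only SAE and immunogenicity data for the final analysis.

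Three stronger readings are tempting but not supported:

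- **That the window contradicts Amendment 2.** The summary of changes has severity assessed at the 7- and 28-day calls "following the recording period specified for these events", and a reader might infer that the calls must come after the period ends. Footnote q, however, applies the unsolicited-AE assessment to the Visit 3 call around Day 8, well inside the 28 days. Read as in line with the recording period, the phrase fits both calls. It also stands in a change log and is not operative text.
- **That rates are certainly biased downward.** Late calls lengthen the post-dose period. SAP Section 5.5.1.1 limits the unsolicited-AE tables to 28 days, so the added days may not offset the loss, but the SAP does not say how the two rules combine.
- **That the rates cannot be compared with other studies.** The documents give no other study's call window.

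It is also fair to say that safety is descriptive and that the window is the same in all three randomized, blinded groups. No decision rule depends on these rates.

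**Conclusion.** The point holds as a gap in scheduled ascertainment of one named secondary endpoint. Up to 7 of 28 days (25%) can pass without scheduled questioning in a participant called on Day 22. The average would be 6.7% with uniform call days over the full window and 3.1% with calls within 3 days of target; both distributions are assumed. The incidence figures also rest on assumed event rates, a constant hazard and no spontaneous reporting, so they are upper illustrations.

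The consequence is possible under-ascertainment of descriptive 28-day rates of non-serious unsolicited AEs, expected to be similar across groups. It gives no reason to expect a distorted comparison between lots and does not touch the primary immunogenicity test. The case for acting is that the remedy costs almost nothing.

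**What to change.** **Protocol Section 1.3 and Section 8 (Visit Windows):** change the Visit 5 window to 0/+7 days (Day 29 to Day 36), and have the call ask about events with onset through 28 days post-vaccination.

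**SAP Section 5.5.1.2, for calls already made before Day 29:** add a sensitivity table of unsolicited AEs with onset within 28 days, restricted to participants whose Visit 5 contact was on or after Day 29. Section 8 already requires actual assessment dates to be recorded, so no new data are needed. The SAP already plans a sensitivity table by e-diary completeness for solicited AEs; this would be its counterpart. The table shows whether early calls matter but cannot recover events that were never reported.

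**Cost:** a one-line change to a telephone window and one extra table, with no added contact. Sites lose 7 days of scheduling flexibility on the early side. The latest permitted call date stays at Day 36.

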8.1. Immunogenicity Assessments

Venous blood samples of approximately 10 mL will be collected for the determination of humoral immune responses at the timepoints indicated in the Schedule of Activities. Sample collection and processing will be performed by the study-site personnel according to current versions of approved standard operating procedures.

The RSV A strain pre-F ELISA antibody titers are the primary (at Day 15) and exploratory (at Month 6) endpoint for this study. In previous studies using the vaccine regimen, high pre-F ELISA titers were commonly associated with high VNA-A2 titers following vaccination.

To complement the

pre-F ELISA responses and further characterize the functional antibody responses, RSV neutralizing antibody responses (VNA-A2) will also be evaluated.

Humoral immunogenicity evaluations are summarized in Table 3.

Table 3: Summary of Immunogenicity Assays (Humoral)

Assay	Purpose
Primary and exploratory endpoints	
F-protein antibodies (RSV-A pre-F ELISA)	Analysis of antibodies binding to RSV-A F-protein in pre-fusion form
Secondary and exploratory endpoints	
RSV A neutralization assay (VNA A2)	Analysis of neutralizing antibodies against the RSV A2 strain

ELISA = enzyme-linked immunosorbent assay; VNA = virus neutralization assay

8.2. Safety Assessments

Safety assessments will include the monitoring of AEs and vital signs.

AEs will be reported and followed by the investigator as specified in Section 8.3 and Appendix 2.

Any clinically significant abnormalities will be followed by the investigator until clinical resolution (return to baseline) or until a clinically stable condition is reached, or until the participant has been deemed lost to follow-up after demonstration of due diligence of follow-up efforts.

The study will include the following evaluations of safety and reactogenicity according to the timepoints provided in the Schedule of Activities.

8.2.1. Physical Examinations

At any clinic visit, an abbreviated, symptom-directed physical examination may be performed if deemed necessary by the investigator based on any clinically relevant issues, clinically relevant symptoms, and medical history.

Physical examinations will be performed by the investigator or appropriately trained delegate. Any clinically relevant abnormalities or changes in severity noted during the review of body systems should be documented in the eCRF as an AE or SAE if it meets the criteria for an AE or SAE according to the protocol reporting requirements.

8.2.2. Vital Signs

Body temperature (oral route preferred), heart rate (beats per minute), respiratory rate (breaths per minute), and systolic and diastolic blood pressure (mmHg) will be measured pre- and post-vaccination. At non-vaccination visits, vital signs will be measured if deemed necessary by the investigator. Height and weight will be measured during screening.

Blood pressure and heart rate measurements will be assessed, if possible, with a completely automated device. Manual techniques will be used only if an automated device is not available.

Sitting systolic and diastolic blood pressure and heart and respiratory rate measurements should be preceded by at least 5 minutes of rest in a quiet setting without distractions (eg, television, cell phones).

Confirmatory vital signs measurement can be performed if inconsistent with a prior measurement. Any abnormalities or changes in severity noted during the review of vital signs should be documented in the eCRF.

